Perform 12-lead ECG	X		X		
Pregnancy test 	X	X	X		
Blood for Hematology: CBC with differential	X		X		
Blood for Chemistry: Sodium, potassium, bicarbonate, glucose, BUN, Cr	X		X		
Study Related Procedures					
Dispense study drug & device, provide training	X				
Collect nasopharyngeal swabs for viral PCR	X	X	X	X	X
Collect serum for viral antibodies	X	X	X	X	
Collect plasma for measurement of quinine		X			
Collect saliva for TAS2R genotyping	X				
Estimated Blood Volume per Visit (mL)	40	25	40	20	

 A targeted physical exam will be performed at Weeks 2, 4 and 6 and at unscheduled visits.

 The participant diary will only be reviewed at Weeks 2 and 4; it will be reviewed and collected at Week 6.

 A urine pregnancy test will be administered.

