## 5.2 Packaging and Labeling

Study product will be supplied in kits labeled only with a randomly generated Treatment Kit #. Each kit will contain 28 vials of study drug (sufficient for 28 days of treatment) with each vial containing 7 mL of study drug. Study product will be stored at the University of Pennsylvania Investigational Drug Service. Vials of drug will be provided packaged in a cardboard box and inside amber plastic bags to reduce UV exposure.

Drug product labels are shown below in **Table 5.2-1**. Labels are generated in tandem as shown: one side to be affixed to each Drug Product kit and the second side as detachable for pharmacy logs. As participants present for randomization, treatment assignments will follow the randomization schema in successive order. The study pharmacist will write the Subject ID# and dispensing date on the two labels at the time of study drug dispensation. The side that had been affixed to the Drug Product Kit will remain, while the other half is detached and affixed into the Pharmacy Log form. As noted, the detachable side for Pharmacy is designated as to whether the vials in the kit contain active drug (GLS-1200) or placebo (0.9% saline).

The randomized Treatment Kit # and the designation as Active or Placebo serve as independent confirmatory checks on treatment assignment.

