#### **5.4 Dispensing of Study Drug**

It is the responsibility of the Investigators that study drug is dispensed only to study participants. Authorized personnel are the only ones to dispense product according to local regulation.

At enrollment, study participants will be provided one kit containing 28 vials of study drug, 28 nasal atomizers, and 84 syringes. Each vial and atomizer will be used for single-day drug administration and then discarded, while a new syringe will be used at each of the three daily administrations and then discarded.

The study pharmacist or study coordinator will demonstrate to participants how to remove drug from the vial into syringes and to self-administer product. Coordinator will also review proper handling and storage conditions for the materials provided. A link will be provided to an instructional video on study drug handling and administration.

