### Start Dates

- If the day portion of the start date is missing, then the start date will be estimated to be equal to the date of IP administration, provided the start month and year are the same as IP administration and the stop date is either after IP administration or completely missing. Otherwise, the missing day portion will be estimated as ‘01’.
- If both the day and month portions of the start date are missing, then the start date will be estimated to be equal to the date of IP administration, provided the start year is the same as IP administration and the stop date is either after IP administration or completely

missing. Otherwise, the event will be assumed to start on the first day of the given year, e.g., 2013-??-?? is estimated as 2013-01-01.

- If the start date is completely missing and the stop date is either after IP administration or completely missing, the start date will be estimated to be the day of IP administration. Otherwise, the start date will be estimated to be the first day of the same year as the stop date. All other non-AE and non-concomitant medication day calculations where only partial dates are available will be handled as follows: the first day of the month will be used in the calculations if the day part of a start date is missing while January 1 will be employed if both the month and day parts of a start date are missing.
- For treatment start dates, if patients are randomized and have non-missing visit data for Week 4 as well as non-missing treatment diary data, then start date is set to earliest treatment diary date. If patient's treatment diary data is missing or Week 4 visit is missing, then treatment start date is set to earliest recorded exposure date. Drug dispensation date is used as treatment start date if no other data is available.

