### **Stop Dates**

- If only the day of resolution is unknown, the day will be assumed to be the last of the month, e.g., 2013-01-?? will be treated as 2013-01-31.
- If both the day and month of resolution are unknown, the event will be assumed to have ceased on the last day of the year, e.g., 2013-??-?? will be treated as 2013-12-31.
- If the stop date is completely missing or the event is continuing, the event will be assumed to be after IP administration and will be left as missing.
- For treatment stop dates, if patient has non-missing treatment diary data but has data gaps of more than 3 days, then treatment stop date is set to start date + 28 days. If treatment diary data is non-missing and there are no data gaps of 3 days or more then treatment stop date is set to last treatment diary date. If treatment diary data is missing but patient is recorded to have completed study, then treatment stop date is set to start date + 28 days. Finally, if treatment diary data is missing and patient has not completed the study, then treatment stop date is set to study withdrawal date.

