## **APPENDIX C: TABLE LAYOUTS**

Table 14.1.1.1  
Subject Disposition  
(All Subjects)

Study Site Subject Status	GLS-1200	Placebo	Overall
Overall			
Screened			xx
Screen Failures			xx
ITT Population [1]	xx	xx	xx
Safety Population [2]	x (xx.x%)	x (xx.x%)	x (xx.x%)
PP Population [3]	x (xx.x%)	x (xx.x%)	x (xx.x%)
Completed the study [4]	x (xx.x%)	x (xx.x%)	x (xx.x%)
Discontinued the study	x (xx.x%)	x (xx.x%)	x (xx.x%)
Reason for discontinuation			
<Reason #1>	x (xx.x%)	x (xx.x%)	x (xx.x%)
<Reason #2>	x (xx.x%)	x (xx.x%)	x (xx.x%)
<Reason #3>	x (xx.x%)	x (xx.x%)	x (xx.x%)
Site 101			
.			
.			
Site 108			
.			
.			

Percentages are based on the ITT Population.

[1] The Intent-to-treat (ITT) Population includes all randomized to treatment allocation.

[2] The Safety Population includes all subjects who received at least one dose of study treatment.

[3] The Per-protocol (PP) Population includes all subjects who completed the trial, received  $\geq 90\%$  of the study treatments, and have no significant protocol deviations. Trial completion is defined as either completing Week 4 or meeting the study endpoint of PCR confirmed SARS-CoV-2 infection.

[4] Study completion is defined as completing all visits regardless of drug compliance.

Reference: Listing 16.2.1

Source: \\xx\\xx\\xx\\xx\\xx\\xxxx\\xxxxxxxxxxxx\\xxxx\\xxxx.sas      date      time

**Programming note:** Sort discontinuation reasons by descending overall frequency. List all reasons per CRF page.

Table 14.1.1.2  
Reason for Screen Failure  
(All Screen Failure Subjects)

Study Site	Reason	Overall (xx)
Overall		
<Reason #1>		x (xx.x%)
<Reason #2>		x (xx.x%)
<Reason #3>		x (xx.x%)
Site 101		
<Reason #1>		x (xx.x%)
<Reason #2>		x (xx.x%)
<Reason #3>		x (xx.x%)
Site 108		
<Reason #1>		x (xx.x%)
<Reason #2>		x (xx.x%)
<Reason #3>		x (xx.x%)

Reference: Listing 16.2.3 and Listing 16.2.1

Source: \\xx\\xxx\\xxx\\xxx\\xxxxxx\\xxxxxxxxxxxx\\xxxx\\xxxxx.sas      date      time

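### For non-completers with no treatment diary, the SAP's treatment stop date has no upper limit, so reported exposure can exceed the 28-day kit; a longest diary gap of exactly 3 days gets no stop date at all

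*SAP*

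**What the plan says.** The last bullet of SAP Appendix A, Stop Dates, has four clauses for the treatment stop date.

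- Diary present, with a gap of more than 3 days: start date + 28 days.
- Diary present, with no gap of 3 days or more: last diary date.
- Diary missing, study completed: if the "patient is recorded to have completed study, then treatment stop date is set to start date + 28 days".
- Diary missing, study not completed: "if treatment diary data is missing and patient has not completed the study, then treatment stop date is set to study withdrawal date".

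Only the last clause has no limit tied to the supply or to the diary.

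Three other places determine who reaches it and what the supply allows.

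- SAP Table 14.1.1.1, footnote [4]: "Study completion is defined as completing all visits regardless of drug compliance". Protocol section 4.4 likewise requires all scheduled treatments and follow-up visits.
- Protocol Table S2, footnote 2, on the participant diary: it is only reviewed at Weeks 2 and 4, and "it will be reviewed and collected at Week 6".
- Protocol section 5.4, on what is handed out on entry to the study: "study participants will be provided one kit containing 28 vials of study drug, 28 nasal atomizers, and 84 syringes". On the rate of use, the same section says: "Each vial and atomizer will be used for single-day drug administration and then discarded".

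Duration of exposure is defined in two ways. SAP section 7.6 takes last dose date minus first dose date. Footnote [1] of Table 14.1.5 and of Listing 16.2.5.1 adds 1.

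**The concern.** Someone who attends Week 4 and is then lost has not completed all visits. If the diary was still to be handed in at Week 6, its data may be missing. That participant falls under the final clause, and any withdrawal date after Week 4 becomes the last treatment date. Someone with the same missing diary who attended every visit stops at start + 28. The participant with less follow-up can thus be credited with more treatment than the one with more, and with more days than one kit supplies.

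Safety and tolerability are a primary objective, and Table 14.1.5 is where a reader looks to see how long each arm was treated. An arm with more late loss to follow-up would show a longer mean and maximum duration for a reason unrelated to dosing.

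**Working it through.** **Supply.** Protocol section 5.4 gives 28 vials at one per day, 28 atomizers at one per day, and 84 syringes at three per day. So 28 / 1 = 28, 28 / 1 = 28 and 84 / 3 = 28 days. This reproduces the 28 days of treatment stated in Protocol section 5.2.

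**Exposure by withdrawal date.** Let the start be Day 0 and withdrawal be dated Day d, with no diary and the study not completed. The stop date is Day d. Duration is d under SAP section 7.6 and d + 1 under Table 14.1.5. A cap at the other clauses' limit replaces d by min(d, 28). Week 4 with its window runs from Day 25 to Day 31, and Week 6 from Day 39 to Day 45.

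| Withdrawal dated | Section 7.6 / Table 14.1.5 | With cap at start + 28 | Days removed by cap |
|---|---|---|---|
| Day 25 (earliest Week 4) | 25 / 26 | 25 / 26 | 0 |
| Day 28 | 28 / 29 | 28 / 29 | 0 |
| Day 31 (latest Week 4) | 31 / 32 | 28 / 29 | 3 |
| Day 35 | 35 / 36 | 28 / 29 | 7 |
| Day 42 (nominal Week 6) | 42 / 43 | 28 / 29 | 14 |
| Day 45 (latest Week 6) | 45 / 46 | 28 / 29 | 17 |

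The comparator, diary missing but all visits attended, gets 28 / 29.

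**Shift in an arm's mean.** The documents give no rate of loss, so the fraction f of an arm in this branch is an assumption, and each such participant is placed at Day 42. The shift due to the missing cap is f × (42 − 28) = 14f, and it is the same under the other formula (43 − 29 = 14).

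- f = 5%: 0.05 × 14 = 0.7 days
- f = 10%: 0.10 × 14 = 1.4 days
- f = 15%: 0.15 × 14 = 2.1 days

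**Gap clauses.** Let g be the longest diary gap in whole days. One clause needs g > 3 and the other needs g < 3. At g = 3 neither applies, and no stop date is defined. This needs no assumption.

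**Where the stop date is used.** It supplies the last dose date for duration of exposure in Table 14.1.5 and Listing 16.2.5.1. Compliance (SAP 7.7) and per-protocol membership (SAP 6.3) use doses recorded in the diary. The treatment-emergent definition (SAP 9.1.4.1) has no end-of-treatment cut-off. The primary endpoint (SAP 8.1) does not use the stop date.

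**The case against.** A reader might infer that anyone lost after Week 4 will be reported with six weeks or more of exposure. The documents do not support that. It needs missing diary data and a withdrawal dated Day 42 or later (Day 41 with the +1 formula). Neither document says whether withdrawal in a lost participant is dated to last contact, to the missed visit or to administrative closure. Dated to the Week 4 visit, the result is 25 to 32 days.

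Entry into the branch also rests on two readings.

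- SAP section 1 lists a Symptom Diary and a Treatment Diary separately, and the Week 6 collection footnote speaks only of the participant diary. Against this, Protocol section 6.8 places exposure history in the participant diary, and SAP section 7.6 lists exposures with treatment diary data, which suggests that the treatment diary is part of it.
- SAP section 6.3 equates end of study with 4 weeks, and Table 14.1.1.1 footnote [3] defines trial completion at Week 4 or at a confirmed infection. On that reading the participant goes to the start + 28 clause. Footnote [4] and Protocol section 4.4 make the all-visits reading more likely, without settling it.

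Three further inferences go too far.

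- *The adverse event analyses are distorted.* They are counts and percentages of subjects with exact intervals, not rates per unit of exposure.
- *A participant with no known dose is credited with weeks of treatment.* SAP Start Dates does say "Drug dispensation date is used as treatment start date if no other data is available", but Table 14.1.5 is restricted to subjects who received at least one dose. Whether such a participant enters it is a question of population membership.
- *The cap would correct early stopping.* For true dosing of 14 days and withdrawal on Day 42, Table 14.1.5 shows 43, which is 29 too many. Capped at start + 28 it shows 29, still 15 too many. That remainder comes from imputing unknown dosing.

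Finally, exposure beyond Day 28 is not strictly impossible. A participant who skipped whole days could have vials left, so any cap is an approximation. The other clauses already accept that approximation.

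These objections limit the size and certainty of the point. They do not explain why one imputing clause should lack the limit that the others have.

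**Conclusion.** The point holds in limited form. The final clause can report more exposure than the 28-day kit covers, and more than is reported for a full attender with the same missing diary. The excess over start + 28 is 7 days for a withdrawal dated Day 35 and 14 days for one dated Day 42. It is nil for a withdrawal dated Day 28 or earlier. The mean shift of 0.7 to 2.1 days rests on an assumed 5% to 15% of an arm in the branch, all dated Day 42. It also rests on the all-visits reading of completion and on the treatment diary being missing when the participant is lost. The hole at a gap of exactly 3 days is certain on the text.

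Severity is minor: one descriptive summary and its listing are affected, and no efficacy, adverse event, compliance or per-protocol result.

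**What to change.** In SAP Appendix A, Stop Dates:

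1. Reword the final clause so that the stop date is the earlier of the study withdrawal date and the supply limit used in the other imputing clauses.
2. Use one convention in all clauses: either start + 27 with the +1 formula (27 + 1 = 28 days) or start + 28 with the formula without +1 (28 days). Changing only the final clause to start + 27 would give 28 days there and 29 in the others under the +1 formula. The first option also agrees with the diary clause: dosing on Days 0 to 27 gives 27 − 0 + 1 = 28, but 27 without the +1.
3. Reconcile SAP section 7.6 with footnote [1] of Table 14.1.5 and of Listing 16.2.5.1. The Standard Calculations in Appendix A already use +1.
4. Make the gap clauses complementary: more than 3 days versus 3 days or less.
5. State which definition of completion the Stop Dates bullet uses, and how withdrawal is dated for participants lost to follow-up.

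The cost is a few sentences and minor programming, with no new data. Reported exposure falls slightly if anyone is in the branch with a late withdrawal date.

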### **Standard Calculations**

Variables requiring calculation will be derived using the following formulas:

- Study Day – The day in relation to the first dose date (Day 0), calculated as date – first dose date.
- Days – A duration expressed in days between two dates (start date and end date) is calculated using the formulas noted below:
  - duration in days = end date – start date + 1, where end date  $\geq$  start date
  - duration in days = end date – start date, where end date  $<$  start date

- Months – A duration expressed in months is calculated as the number days divided by 365.25/12 (~30.4).
- Years – A duration expressed in years between one date (date1) and another later date (date2) is calculated using the formula: duration in years = (date2-date1+1)/365.25
- Height – Height entries made in inches (in) are converted to centimeters (cm) using the following formula: height (cm) = height (in)  $\times$  2.54
- Weight – Weight entries made in pounds (lb.) are converted to kilograms (kg) using the following formula: weight (kg) = weight (lb.) / 2.2046
- Temperature – Temperature entries in degrees Fahrenheit are converted to degrees centigrade using the following formula: temp (degrees centigrade) =  $5/9 \times [\text{temp (degrees Fahrenheit)} - 32]$
- Change from baseline – Change from baseline will be calculated as: Change = post baseline value – baseline value
- Percent change from baseline – Change from baseline will be calculated as: percent change from baseline =  $[(\text{post baseline value} - \text{baseline value}) / \text{baseline value}] \times 100$

**APPENDIX B: TABLE OF CONTENTS FOR STATISTICAL TABLES AND LISTINGS**

The following TL numbering is completed according to ICH guidelines. The ICH heading number and description are in **bold**. Minor changes from this planned index do not need to be amended in the SAP. Formal organization of tabulations may be changed during programming if appropriate, e.g., tables for the different variables may be combined into a single table, or tables with more than one variable may be split into several tables.

**List of Tables**

ICH Heading	Table Number	Table Description
14.1		DEMOGRAPHIC/BASELINE DATA
	14.1.1.1	Subject Disposition (All Subjects)
	14.1.1.2	Reason For Screen Failure (All Screen Failure Subjects)
	14.1.2	Demographic and Baseline Characteristics (Safety Population)
	14.1.3	Medical History (Safety Population)
	14.1.4	Concomitant Medications (Safety Population)
	14.1.5	Exposure and Treatment Compliance (Safety Population)
14.2		EFFICACY DATA
	14.2.1.1	Incidence of SARS-CoV-2 Infection by Visit (ITT Population)
	14.2.1.2	Incidence of SARS-CoV-2 Infection by Visit (PP Population)
	14.2.2	Incidence of Individual Symptoms and Average Number of Days with Symptoms by Visit Interval (ITT Population)
	14.2.3	Cumulative Incidence of SARS-CoV-2 Seroconversion by Visit (ITT Population)
14.3		SAFETY DATA
14.3.1		Displays of Adverse Events
	14.3.1.1	Overall Summary of Adverse Events (Safety Population)
	14.3.1.2	Treatment-Emergent Adverse Events by System Organ Class and Preferred Term (Safety Population)
	14.3.1.3	Treatment-Emergent Adverse Events by System Organ Class, Preferred Term, and Strongest Relationship to Study Drug (Safety Population)
	14.3.1.4	Treatment-Emergent Adverse Events by System Organ Class, Preferred Term, and Maximum Severity Grade (Safety Population)
	14.3.1.5	Related Treatment-Emergent Adverse Events by System Organ Class, Preferred Term, and Maximum Severity Grade (Safety Population)
14.3.2		Serious and Significant Adverse Events
	14.3.2.1	Serious Adverse Events by System Organ Class and Preferred Term (Safety Population)
	14.3.2.2	Serious Treatment-Emergent Adverse Events by System Organ Class and Preferred Term (Safety Population)

ICH Heading	Table Number	Table Description
	14.3.2.3	Treatment-Emergent Adverse Events Leading to Study Discontinuation by System Organ Class and Preferred Term (Safety Population)
	14.3.2.4	Treatment-Emergent Adverse Events Leading to Death by System Organ Class and Preferred Term (Safety Population)
14.3.4		Laboratory
	14.3.4.1	Shift from Baseline in Hematology Results by Test and Visit (Safety Population)
	14.3.4.2	Shift from Baseline in Chemistry Results by Test and Visit (Safety Population)
	14.3.4.3	Observed and Change from Baseline in Vital Sign Results by Test and Visit (Safety Population)
	14.3.4.4.1	Shift from Baseline in 12-Lead ECG Overall Interpretation by Visit (Safety Population)
	14.3.4.4.2	Summary of QTcF Interval (msec) by Visit and Result Category (Safety Population)

## List of Figures

ICH Heading	Figure Number	Figure Description
14.3.4		Laboratory
	14.3.4.1	Line Plots of Mean (+/- SD) Hematology Results vs. Time by Test (Safety Population)
	14.3.4.2	Line Plots of Mean (+/- SD) Chemistry Results vs. Time by Test (Safety Population)
	14.3.4.3	Line Plots of Mean (+/- SD) Vital Sign Results vs. Time by Test (Safety Population)
	14.3.4.4	Line Plots of Mean (+/- SD) 12-Lead ECG Results vs. Time by Test (Safety Population)

## List of Data Listings

ICH Heading	Listing Number	Listing Description
16.2		SUBJECT DATA LISTINGS
16.2.1		Discontinued Subjects
	16.2.1	Subject Disposition
16.2.2		Protocol Deviations
	16.2.2	Protocol Deviations
16.2.3		Subjects Excluded from the Safety Analysis
	16.2.3	Inclusion/Exclusion Criteria
16.2.4		Demographic and Baseline Data
	16.2.4.1	Demographic and Baseline Characteristics
	16.2.4.2	Medical History
	16.2.4.3	Prior and Concomitant Medications
16.2.5		Compliance and/or Drug Concentration Data
	16.2.5.1	Exposure and Treatment Compliance
	16.2.5.2	Treatment Diary
	16.2.5.3	Plasma Collection for Measurement of Quinine
16.2.6		Individual Efficacy Response Data
	16.2.6.1	PCR Results
	16.2.6.2	Symptom Scores
	16.2.6.3	Seroconversion
16.2.7		Adverse Events listings
	16.2.7.1	Adverse Events
	16.2.7.2	Serious Adverse Events
	16.2.7.3	Adverse Events Leading to Study Discontinuation
	16.2.7.4	Deaths
16.2.8		Laboratory and Other Data
	16.2.8.1	Hematology
	16.2.8.2	Chemistry
	16.2.8.3	Vital Signs
	16.2.8.4	12-Lead Electrocardiogram
	16.2.8.5	Physical Examination
	16.2.8.6	Pregnancy Test

## **APPENDIX C: TABLE LAYOUTS**

Table 14.1.1.1  
Subject Disposition  
(All Subjects)

Study Site Subject Status	GLS-1200	Placebo	Overall
Overall			
Screened			xx
Screen Failures			xx
ITT Population [1]	xx	xx	xx
Safety Population [2]	x (xx.x%)	x (xx.x%)	x (xx.x%)
PP Population [3]	x (xx.x%)	x (xx.x%)	x (xx.x%)
Completed the study [4]	x (xx.x%)	x (xx.x%)	x (xx.x%)
Discontinued the study	x (xx.x%)	x (xx.x%)	x (xx.x%)
Reason for discontinuation			
<Reason #1>	x (xx.x%)	x (xx.x%)	x (xx.x%)
<Reason #2>	x (xx.x%)	x (xx.x%)	x (xx.x%)
<Reason #3>	x (xx.x%)	x (xx.x%)	x (xx.x%)
Site 101			
.			
.			
Site 108			
.			
.			

Percentages are based on the ITT Population.

[1] The Intent-to-treat (ITT) Population includes all randomized to treatment allocation.

[2] The Safety Population includes all subjects who received at least one dose of study treatment.

[3] The Per-protocol (PP) Population includes all subjects who completed the trial, received  $\geq 90\%$  of the study treatments, and have no significant protocol deviations. Trial completion is defined as either completing Week 4 or meeting the study endpoint of PCR confirmed SARS-CoV-2 infection.

[4] Study completion is defined as completing all visits regardless of drug compliance.

Reference: Listing 16.2.1

Source: \\xx\\xx\\xx\\xx\\xx\\xxxx\\xxxxxxxxxxxx\\xxxx\\xxxx.sas      date      time

**Programming note:** Sort discontinuation reasons by descending overall frequency. List all reasons per CRF page.

Table 14.1.1.2  
Reason for Screen Failure  
(All Screen Failure Subjects)

Study Site	Reason	Overall (xx)
Overall		
<Reason #1>		x (xx.x%)
<Reason #2>		x (xx.x%)
<Reason #3>		x (xx.x%)
Site 101		
<Reason #1>		x (xx.x%)
<Reason #2>		x (xx.x%)
<Reason #3>		x (xx.x%)
Site 108		
<Reason #1>		x (xx.x%)
<Reason #2>		x (xx.x%)
<Reason #3>		x (xx.x%)

Reference: Listing 16.2.3 and Listing 16.2.1

Source: \\xx\\xxx\\xxx\\xxx\\xxxxxx\\xxxxxxxxxxxx\\xxxx\\xxxxx.sas      date      time

